Part 3 (Cohorts 5 to 6; dose-escalation and evaluation of two doses of GT005 delivered with the Orbit SDS; subretinal delivery via a suprachoroidal cannulation) will enrol three to five subjects at the mid dose ([REDACTED] vg; Cohort 5) and three to five subjects at the high dose ([REDACTED] vg; Cohort 6), to evaluate the safety of GT005 treatment when delivered via the Orbit SDS. Part 3 (Cohorts 5 to 6) is independent of, and may be conducted in parallel to, Part 2 (Cohort 4). Dose-escalation will be evaluated by the DSMB and will be assessed based on the Week 5 safety data for the first three subjects dosed in Cohort 5.

Part 4 (Cohort 7) dose-expansion of GT005 delivered with the Orbit SDS; subretinal delivery via a suprachoroidal cannulation) will enrol up to 20 subjects in Cohort 7 to further characterise the safety, dose response, and efficacy of GT005 treatment when delivered via the Orbit SDS. On completion of dose-escalation, dose levels determined to be safe and tolerable by the DSMB in Part 1 (Cohorts 1 to 3) may be assessed in Cohort 7. The exact number of subjects that will be enrolled in Cohort 7 will be determined by the Sponsor based on the emerging safety, pharmacodynamic and clinical outcomes data.

The study treatment consists of an AAV2 expressing hCFI. The treatment is administered as a single subretinal injection into one eye – “the study eye”. Both eyes will be assessed at the screening visit. If both eyes meet the eligibility criteria the study eye will be the worse seeing eye or the eye with the largest GA size for eyes with equivalent visual acuity unless the patient (in consultation with the surgeon) expresses an alternative preference.

The study will, for the individual subjects, consist of up to 13 visits over a 5-year period. All subjects will be assessed for the occurrence of adverse events (AEs) at each visit and will undergo functional visual and retinal imaging/anatomical assessments and biological sampling as per the schedule of assessments.

Objectives	Evaluation Criteria
Primary	

To evaluate the safety of GT005 at 3 doses	
Incidence of ocular and non-ocular treatment-emergent AEs (TEAEs) and treatment-emergent serious AEs (TESAEs) over 48 weeks
Secondary	

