3. STUDY DESIGN

3.1. Overall Study Design and Plan Description

This is an open label FIH Phase I/II multicentre study to evaluate the safety, dose response and efficacy of GT005 in subjects with GA due to AMD. The study will be conducted in four parts; Part 1 (Cohorts 1 to 3): dose-escalation, Part 2 (Cohort 4): dose-expansion, Part 3 (Cohorts 5 to 6): dose-escalation with the Orbit SDS, and Part 4 (Cohort 7): dose-expansion with the Orbit SDS.

Parts 1 and 2 (Cohorts 1 to 4) will deliver GT005 via the standard transvitreal procedure and Parts 3 and 4 (Cohort 5 to 7) will deliver GT005 via the Orbit SDS.

The Orbit SDS is a 510(k) cleared device in the US whereby Parts 3 and 4 (Cohorts 5 to 7) will only be used at US sites.

An overview of the study design is provided in [Figure 1: Overview of the Study]. Approximately 65 subjects will be enrolled: up to five in each of Cohorts 1 to 3, up to 20 in Cohort 4, up to five in each of Cohorts 5 and 6, and up to 20 in Cohort 7.

Part 1 (Cohorts 1 to 3; dose-escalation) will test three dose Cohorts (████████████ vg) of up to five subjects per Cohort. A minimum of three subjects per dose Cohort will be required to evaluate the safety of the respective dose. Sentinel dosing will be applied whereby there will be a minimum of 14 days separation between dosing of the first and second subject of each dose Cohort, to assess any acute reactions to surgery and short-term tolerability to GT005 prior to dosing the remaining subjects in each dose Cohort. Dose escalation will be evaluated by a DSMB and will be assessed based on the Week 5 data for the first three subjects dosed in Cohorts 1 and 2. The DSMB will review the Week 5 safety data for the first three subjects dosed in Cohort 3 prior to dosing in further cohorts. The DSMB can be called upon by the Sponsor to perform safety evaluations as needed.

Subjects will receive a single subretinal injection of GT005 at one of three dose levels:

- Low dose: ██████████
- Mid dose: ██████████
- High dose: ██████████

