Part 2 (Cohort 4; dose-expansion) will enrol up to 20 subjects in Cohort 4 with GT005 delivered via the transvitreal procedure to further characterise the safety, dose response and efficacy of GT005. On completion of dose escalation, dose levels determined to be safe and tolerable by the DSMB in Part 1 (Cohorts 1 to 3), may be assessed in Cohort 4. The exact number of subjects that will be enrolled in Cohort 4 will be determined by the Sponsor based on the emerging safety, pharmacodynamic and clinical outcomes data.

Part 3 (Cohort 5 to 6; dose-escalation and evaluation of two doses of GT005 delivered with the Orbit SDS; subretinal delivery via a suprachoroidal cannulation) will enrol three to five subjects at the mid dose (████ vg; Cohort 5) and three to five subjects at the high dose (████ vg; Cohort 6), to evaluate the safety of GT005 treatment when delivered via the Orbit SDS. Part 3 (Cohorts 5 to 6) is independent of, and may be conducted in parallel to, Part 2 (Cohort 4). Dose-escalation will be evaluated by the

DSMB and will be assessed based on the Week 5 safety data for the first three subjects dosed in Cohort 5.

Part 4 (Cohort 7; dose-expansion of GT005 delivered with the Orbit SDS; subretinal delivery via a suprachoroidal cannulation) will enrol up to 20 subjects in Cohort 7 to further characterise the safety, dose response, and efficacy of GT005 treatment when delivered via the Orbit SDS. On completion of dose-escalation, dose levels determined to be safe and tolerable by the DSMB in Part 1 (Cohorts 1 to 3) may be assessed in Cohort 7. The exact number of subjects that will be enrolled in Cohort 7 will be determined by the Sponsor based on the emerging safety, pharmacodynamic and clinical outcomes data.

Analyses of data from the Orbit SDS will be based on data accumulated from US sites.

The study treatment consists of an AAV2 expressing hCFI. The treatment is administered as a single subretinal injection into one eye – “the study eye”. Both eyes will be assessed at the screening visit. If both eyes meet the eligibility criteria the study eye will be the worse seeing eye or the eye with the largest GA size for eyes with equivalent visual acuity unless the subject (in consultation with the surgeon) expresses an alternative preference.

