11.3. Statistical Analysis

The detailed statistical analyses will be outlined in the SAP.

The main analysis will be performed at the conclusion of the study (Week 240), after which a clinical study report (CSR) will be prepared. Interim analyses may be considered to help inform internal development decision points for GT005, in which case the details will be pre-specified in the SAP prior to conducting the analysis. Additionally, a safety focused analysis will be conducted to enable the independent data review by a DSMB after three subjects in Cohorts 1 to 3 and Cohort 5 have completed the 5-week post-surgery visit. Additional DSMB meetings may be held as needed or as requested by the DSMB members. Full details can be found in the DSMB Charter.

Analyses of data involving the Orbit SDS is US-specific.

For the main statistical analysis and CSR, all efficacy (anatomical and functional visual outcomes) and safety data will be listed and summarised using descriptive statistics by dose and route of administration, and by assessment (Visits 1 to 8). The Long-term follow-up data (Visits 9 to 13) will be reported separately using descriptive statistics by dose and route of administration and by assessment. Additionally, for all ocular evaluations and tests, and ocular AEs, where appropriate these will be additionally presented by eye (Treated [Study Eye]/Untreated [Fellow Eye]). The descriptive summary for the categorical variables will include subject counts (n) and percentages and, if appropriate, frequency of events. The descriptive summary for the continuous variables will include counts (n), means, medians, standard deviations and minimum and maximum values. Where possible, all data from subjects who withdraw prematurely from the study will be included in any presentations. Further details on the handling of withdrawals and/or missing data will be specified in the SAP.

Subgroup analyses will be performed, if appropriate, to evaluate some of the efficacy endpoints across subgroups defined by genetic classification: e.g., a rare variant resulting in CFI haploinsufficiency and those without.

Graphical displays appropriate to the types of data may be used to present any important findings.

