24. STUDY COMMITTEES

24.1. DATA SAFETY MONITORING BOARD

Composition

A DSMB will be formed to review all safety data at predetermined intervals during the study. Additional DSMB meetings may be held as needed or as requested by the DSMB members. The DSMB will comprise of at least three individuals who cumulatively have the clinical and medical expertise to monitor the safety of subjects in the clinical study and will include a minimum of one clinician expert in the management of AMD and clinical immunology. The DSMB will be chaired by one of the clinical experts who will attend all meetings. No DSMB member will be an Investigator in this study.

Roles and Responsibilities of DSMB

The roles and responsibilities of the DSMB are defined in the DSMB Charter, which include, but are not limited to:

- Monitoring and reviewing all safety issues relative to the conduct of the study
- Ensuring the protection and safety of subjects participating in the study
- Recommending dose escalation in accordance with available safety data and study stopping rules
- Recommending a different BCVA threshold for entry into the study
- Providing recommendations to continue, modify the design, suspend or terminate the study depending upon emerging safety data
- Communicating other recommendations or concerns as appropriate

Dose Escalation

- The DSMB will meet after the third subject has been enrolled (recruitment and treatment will continue – there will be no study hold) and provided Week 5 data in Cohorts 1 to 3, and in Cohort 5
- If treatment has been tolerated and stopping rules have not been met, the DSMB will recommend to Gyroscope that enrolment of the next study Cohort can commence
- Screening of potential subjects will be allowed prior to the DSMB meeting and decision, but treatment must not be administered to subjects in the higher dose group until the outcome of the DSMB recommendation has been provided in writing to Gyroscope

Change to Inclusion Criteria

The DSMB will meet after the third subject has been enrolled (recruitment and treatment will continue – there will be no study hold) and the possibility of raising the BCVA threshold for inclusion in the study at the respective dose-level will be assessed based on Week 5 safety data for the first three subjects dosed in Cohorts 1 and 3.

DSMB Stopping Rules

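### Cohort 7 (Orbit) dose levels are cleared on transvitreal findings alone, and no named Week 5 DSMB review covers Cohort 6, the only earlier test of the high dose by Orbit

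*Protocol*

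**What the plan says.** Protocol Section 3.1 assigns the transvitreal route to Parts 1 and 2 (Cohorts 1 to 4) and the Orbit SDS to Parts 3 and 4 (Cohorts 5 to 7). Part 3 enrols three to five subjects at the mid dose (Cohort 5) and three to five at the high dose (Cohort 6), "to evaluate the safety of GT005 treatment when delivered via the Orbit SDS". Part 4 (Cohort 7) then expands by Orbit to up to 20 subjects.

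The criterion for doses in Cohort 7 appears in the Synopsis and in Section 3.1: "dose levels determined to be safe and tolerable by the DSMB in Part 1 (Cohorts 1 to 3) may be assessed in Cohort 7". It repeats the Part 2 criterion for Cohort 4, which begins "On completion of dose escalation, dose levels determined to be safe and tolerable by the DSMB in Part 1 (Cohorts 1 to 3), may be" and then names that cohort.

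The named DSMB reviews are as follows.

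- Part 1 (Section 3.1): escalation after Cohorts 1 and 2 rests on Week 5 data. For the last step, "The DSMB will review the Week 5 safety data for the first three subjects dosed in Cohort 3 prior to dosing in further cohorts". The same section adds: "A minimum of three subjects per dose Cohort will be required to evaluate the safety of the respective dose".
- Part 3 (Section 3.1): escalation "will be assessed based on the Week 5 safety data for the first three subjects dosed in Cohort 5".
- Section 11.3: the safety analysis for the DSMB is run "after three subjects in Cohorts 1 to 3 and Cohort 5 have completed the 5-week post-surgery visit".
- Section 24.1: the DSMB meets once the third subject has been enrolled "and provided Week 5 data in Cohorts 1 to 3, and in Cohort 5". The Synopsis names the same cohorts.

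**The concern.** The rule for Cohort 7 asks for a DSMB finding from a part of the study that used the other route. The protocol treats route as relevant to safety. Section 2 makes Orbit safety a separate secondary objective, and Section 9.4 attributes procedure-related adverse events to the transvitreal or the Orbit procedure. Part 1 therefore cannot supply any Orbit-procedure events.

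Cohort 6 is enrolled to show whether the high dose is safe by Orbit, but no visible provision makes any decision depend on the answer. Cohort 3, the top transvitreal cohort, does have a review that must precede further dosing.

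The stakes are raised by Section 4.4, which says that GT005 cannot be taken out once injected. Section 1.9 adds that subjects in Parts 2 to 4 are expected to have better preserved vision than those in Part 1.

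**Working it through.** The plan gives no sample size or error rate on this point, so there is no figure to reproduce. The check sets the texts side by side and adds simple arithmetic for scale.

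**1. Which cohorts have a named review before expansion?** Dose values are redacted. Cohort 3 is taken as the high dose because it is the last of three escalating cohorts.

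| Cohort | Route | Dose | Named Week 5 DSMB review |
|---|---|---|---|
| 1, 2 | Transvitreal | The two lower steps | Yes |
| 3 | Transvitreal | High | Yes, before further cohorts |
| 5 | Orbit | Mid | Yes |
| 6 | Orbit | High | None visible |

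Four of the five pre-expansion cohorts are covered. The high dose is reviewed (Cohort 3) and the Orbit route is reviewed (Cohort 5). What goes unreviewed is the combination of the two.

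**2. Does another provision close the gap?**

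- *Completion of escalation.* Part 3 is also labelled dose-escalation, so the opening words of the Cohort 7 sentence may place Cohort 7 after Cohort 6. That fixes the order but requires no finding. Section 1.9 uses the same term for Part 1 alone, so even the order is not certain.
- *Written hold (Synopsis and Section 24.1).* It bars treatment at a higher dose until the DSMB's recommendation is given in writing, while treatment at the current dose continues. High-dose Cohort 7 is at the same dose as Cohort 6, so by its wording the hold does not apply.
- *Stopping rule (Section 24.1).* It covers toxicity related to route, but its stated action is to stop escalation. After Cohort 6 there is no escalation left to stop.

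**3. How many subjects are concerned?** The cohort maxima give 3×5 + 20 + 2×5 + 20 = 65. Only high-dose Cohort 7 subjects are affected. Their number is not stated, so the range is 0 to 20, and 20/65 = 30.8%.

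**4. What would a Cohort 6 review add?** The named reviews now put 3 Orbit subjects before the DSMB, all at the mid dose, and no high-dose Orbit subjects. Adding the first three of Cohort 6 makes this 6 and 3.

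With no events in n subjects, the one-sided 95% upper bound on the event rate is 1 − 0.05^(1/n):

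- n = 3: 1 − 0.05^(1/3) = 63.2%
- n = 6: 1 − 0.05^(1/6) = 39.3%

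The n = 6 figure pools the two doses, so it holds only if the event rate does not depend on dose. For the high dose by Orbit alone, the review moves from no subjects to a bound of 63.2% if no event is seen.

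**5. What can three subjects detect?** The chance of at least one event is 1 − (1 − p)³. The rates p are assumed and do not come from the documents.

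| Assumed rate p | At least one event in 3 | Missed |
|---|---|---|
| 10% | 27.1% | 72.9% |
| 20% | 48.8% | 51.2% |
| 30% | 65.7% | 34.3% |

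**6. How long is the wait?** The Week 5 visit may fall up to 3 days late, so 5×7 + 3 = 38 days from dosing of the third Cohort 6 subject, plus meeting time.

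**The case against.** The strongest objection is that the gap may lie in the sources rather than in the plan. Figure 1 is not shown, its abbreviation key includes the DSMB, and the protocol sends review details to a charter that is not among the documents. Either could already place a review between Cohorts 6 and 7. This stands as a limit. It would reduce the fix to a wording correction, because the Part 4 criterion would still cite Part 1 only.

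The second objection is that protections already reach Cohort 6. The DSMB reviews all safety data at predetermined intervals, may meet at any time and may recommend changing or suspending the study (Section 24.1). Serious events are reported within 24 hours (Section 9.8), and the Sponsor sets the size of Cohort 7 on emerging safety data. All of this is true and lowers the risk. None of it is a set condition for high-dose Orbit expansion.

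The third is that the Cohort 3 comparison is imperfect. Its review also informs a change in the visual acuity threshold, and the eligible population widens after Part 1. Cohorts 4 to 7 share one acuity rule. That is fair, although Cohort 7 drops the upper limit on lesion size.

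Finally, the remaining risk is narrow. Dose and route are each reviewed, the injection volume is the same, and Section 1.6.1.3 describes the inflammation and transient vision loss risks as identical for Orbit. No mechanism for a dose-by-route interaction is put forward. This supports treating the point as an inexpensive improvement, not as a claim that subjects are unprotected.

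**Conclusion.** The concern holds for the text available. The stated criterion for Cohort 7 does not match its route, and every visible list of named Week 5 reviews omits Cohort 6. The gap is limited to the high dose by Orbit and affects 0 to 20 subjects.

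The benefit of closing it is modest. It brings three high-dose Orbit subjects to a named review where there are now none, and such a review would miss a toxicity with a true rate of 10% about 73% of the time. The sponsor already accepts that standard for Cohorts 1, 2, 3 and 5. The pooled 39% bound carries little weight, because it assumes away the dose effect at issue. No number of averted events is claimed.

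The conclusion assumes that neither the charter nor Figure 1 schedules a Cohort 6 review, and that some high-dose Cohort 7 dosing is still ahead. The documents do not give enrolment status. SAP Section 3.1 plans Week 48 Orbit data for the second interim, and the SAP history has an update dated 28 June 2023 in preparation for that lock. Much of the dosing may therefore be complete.

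**What to change.** 1. In the Part 4 sentence (Synopsis and Section 3.1), make the dose criterion depend on the DSMB's finding in Part 1 and, for the Orbit route, on its finding in Part 3: Cohort 5 for doses up to mid, Cohort 6 for the high dose.
2. In the DSMB review lists (Synopsis, Sections 3.1, 11.3 and 24.1), require the DSMB to review Week 5 safety data on the first three Cohort 6 subjects and to recommend in writing before any Cohort 7 subject is given the high dose.
3. Optionally, extend the stopping rule's action in Section 24.1 to cover expansion at the affected dose and route.

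If the charter or Figure 1 already provides the review, only the first edit and a cross-reference are needed. If high-dose Cohort 7 dosing is finished, the clinical study report should state which DSMB review preceded it.

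The cost is at most one more DSMB meeting and, for high-dose Cohort 7 only, a wait of up to 38 days plus meeting time. Doses up to mid can start on the existing Cohort 5 review. No visit or assessment is added. The change is probably a substantial amendment under Section 14.1, needing IRB/REC approval and notification of the Competent Authority. It can be bundled with another amendment.

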4. SUBJECT SELECTION CRITERIA

4.1. Subject Recruitment

Subjects will be recruited from the population of outpatients at the study sites. Potentially eligible subjects interested in taking part in the study may be referred from other sites.

The Investigator will keep records of all subjects screened and included. The reason for screen failure should be stated for all subjects screened but not included. Subjects who are eligible but do not receive treatment with GT005 will be classed as screen failures and may be replaced. The reason for withdrawal should be stated for all subjects included but not completed.

4.2. Inclusion Criteria

For inclusion in the study, subjects must fulfil all of the following criteria:

1. Able and willing to give consent to study participation
2. Have a clinical diagnosis of GA secondary to AMD in the study eye, as determined by the Investigator, and a diagnosis of AMD in the contralateral eye (except if the subject is monocular)
3. Cohorts 1 to 6: GA lesion(s) total size in the study eye must be $\geq 1.25\text{mm}^2$ and $\leq 17.5\text{mm}^2$
Cohort 7: GA lesion(s) total size in the study eye must be $\geq 1.25\text{mm}^2$
4. GA lesion(s) in the study eye must reside completely within the FAF fundus image
5. Cohorts 1 to 3: BCVA of ≤ 50 letters (6/36 Snellen acuity equivalent or worse) using ETDRS charts in the study eye
Cohorts 4 to 7: BCVA of ≥ 24 letters (6/95 and 20/320 Snellen acuity equivalent or better) using ETDRS charts in the study eye
6. Aged ≥ 55 years
7. Able to attend all study visits and complete the study procedures
8. Women of child-bearing potential need to have a negative urine pregnancy test within two weeks prior to receiving the drug. A pregnancy test is not required for postmenopausal women (defined as being at least 12 consecutive months without menses) or those surgically sterilised (those having a bilateral tubal ligation/bilateral salpingectomy, bilateral tubal occlusive procedure, hysterectomy, or bilateral oophorectomy)

4.3. Exclusion Criteria

Subjects must not enter the study if any of the following exclusion criteria are fulfilled:

1. Have evidence or history of CNV in the study eye. Subjects are permitted to have CNV in the fellow eye defined as either:
 - a. Non-exudative/sub-clinical fellow eye CNV identified at screening, or

- b. Known history of fellow eye CNV with either ≥ 2 years since diagnosis or with no active treatment required in 6 months prior to screening
- 2. Presence of moderate/severe non-proliferative, diabetic retinopathy or worse in the study eye
- 3. Have history of vitrectomy, sub-macular surgery, or macular photocoagulation in the study eye
- 4. History of intraocular surgery in the study eye within 12 weeks prior to Screening (Visit 1). [REDACTED]
- 5. Have clinically significant cataract that may require surgery during the study period in the study eye
- 6. Presence of moderate to severe glaucomatous optic neuropathy in the study eye; uncontrolled IOP despite the use of more than two topical agents; a history of glaucoma-filtering or valve surgery is also excluded
- 7. Axial myopia of greater than -8 diopters in the study eye
- 8. Have received any investigational product for the treatment of GA within the past 6 months or 5 half-lives (whichever is longer), other than nutritional supplements such as the age-related eye disease study (AREDS) formula
- 9. Have received a gene or cell therapy at any time
- 10. Have a contraindication to the specified protocol corticosteroid regimen
- 11. Are unwilling to use two forms of contraception (one of which being a barrier method) for 90 days post-dosing, if relevant
- 12. Active malignancy within the past 12 months, except for: Appropriately treated carcinoma in situ of the cervix, non-melanoma skin carcinoma, or prostate cancer with a stable prostate-specific antigen (PSA) ≥ 12 months
- 13. Have any other significant ocular or non-ocular medical or psychiatric condition which, in the opinion of the Investigator, may either put the subject at risk or may influence the results of the study
- 14. Cohorts 5 to 7 only: presence of metallic objects or implanted stimulator devices in or near the head, including cochlear implants, deep brain stimulators, vagus nerve stimulators, and other implanted electrodes or stimulators

